Study Procedures: Patients were initially screened for inclusion and exclusion criteria at their consultation appointment at the University of Washington School of Dentistry graduate endodontic clinic. If the patient met the inclusion criteria, they were asked if they wanted to participate in the study. If they agreed to participate, the research consent forms were signed, and they were given a questionnaire prior to the start of their root canal treatment to rate the pain they were experiencing on a numerical rating scale. At the end of a root canal appointment, it is common to administer additional local anesthetic to keep the tooth numb for a period of time and in order to decrease the amount of post-operative pain a patient could experience even after the anesthetic wears off. However, there is no evidence that supports the use of one anesthetic solution over the other, which is what this study aims to find. Patients were randomized into either the Bupivacaine group (long-acting anesthetic) or Lidocaine (short-acting anesthetic) group. The patients were assigned a research number, which was used for the remainder of the study. The resident treating the patient reconfirmed the diagnosis of the tooth prior to the start of treatment and if the diagnosis changed (i.e.. if the tooth did not have pulpitis and the nerve was dead), the patient was not included in the study. Root canal treatment was initiated using routine root canal procedures, which includes local anesthetic to get the tooth numb and application of a dental dam for isolation. The root canal space was cleaned, and the inflamed nerve removed. An inter appointment medication was placed in the root canals and the root canal access (hole on the biting surface of the tooth) was restored with a temporary filling material to avoid food getting impacted into this space. Following this, the patient received the local anesthetic that they were randomly assigned to: 1 carpule (1.7 mL) of 0.5% Bupivacaine with 1:200,000 epinephrine (long-acting anesthetic), or 1 carpule (1.7 mL) of 2% Lidocaine with 1:100,000

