epinephrine (short-acting anesthetic). The patient was handed the questionnaire (the one they used prior to the start of the appointment) and asked to rate their pain scale on a similar numerical scale at different time intervals after treatment (6, 12, 24, 48, 72 hours). This questionnaire/pain tracking form did not add any time to their root canal procedure, and took 5-10 minutes per day for the patient to fill out while at home in the 72 hours following treatment. The time and date were written on the questionnaire for each individual patient so they could remember to rate their pain at these intervals. The patients were also instructed to take 600 mg of Ibuprofen (Advil) every 6 hours for post-operative pain if needed and asked to document this (how many times a day, how many days) on the questionnaire. Patients were encouraged to track their post-operative pain levels. The patients were instructed to bring this questionnaire back with them when they came back to the clinic to get their root canal treatment completed. At the second treatment appointment, the questionnaire was collected from them and documented and the root canal treatment was completed at this appointment as it would be done for any patient not participating in the study.

Data Analysis: Data were analyzed using SigmaPlot (Grafiti LLC, Palo Alto, CA) for all statistical analyses. Intergroup comparisons were analyzed using a two-sample t-test, intragroup comparisons using a Wilcoxon signed-rank test, post-operative analgesic consumption comparisons using the Fisher Exact Test, and comparisons between male and female post-operative pain levels using the chi-square test.

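### Male-female pain is compared by chi-square although pain is recorded as a numerical score, with no bands, cut-point or hour stated (minor)

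*Combined protocol and SAP*

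**What the plan says.** Under Study Procedures, patients first "rate the pain they were experiencing on a numerical rating scale" before treatment. Afterwards they were asked to "rate their pain scale on a similar numerical scale at different time intervals after treatment (6, 12, 24, 48, 72 hours". The outcome is therefore a numerical score with five post-operative values per patient. The end points of the scale are not given.

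The Data Analysis section lists: "Intergroup comparisons were analyzed using a two-sample t-test, intragroup comparisons using a Wilcoxon signed-rank test". It then names Fisher's exact test for analgesic use and, last, "comparisons between male and female post-operative pain levels using the chi-square test".

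Nothing in the combined document groups the scores into bands, sets a cut-point, or says which of the five ratings (or what summary of them) enters the sex comparison. The phrase for pain levels also appears under Study Procedures, "Patients were encouraged to track their post-operative pain levels", where it refers to what patients entered on the questionnaire, that is, the numerical ratings.

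**The concern.** Chi-square needs categories, and the plan collects scores. Some step between the two is missing, and the meaning of the test depends on that step.

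- **Three or more categories.** Pearson chi-square treats them as unordered labels. A small p-value says that the distributions differ by sex. It does not say that one sex has more pain.
- **Two categories.** The ordering problem disappears, because a difference in one proportion has a direction. But the scores on each side of the cut are merged, and the p-value can fall on either side of 0.05 depending on a cut that is not stated.

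In both cases a reader cannot reproduce the test, and a bare p-value for sex is hard to interpret. The missing hour adds to this, although the intergroup t-test has the same gap.

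**Working it through.** The plan has no figure to reproduce: it states no sample size, alpha, power, SD or effect size. The check therefore has one exact part and one illustrative part.

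**1. Order (exact arithmetic, invented counts).** Take 30 men and 30 women in four ordered bands.

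- Table A: 12/9/6/3 against 3/6/9/12. Every column totals 15, so every expected count is 7.5. Chi-square = 2 × (4.5² + 1.5² + 1.5² + 4.5²)/7.5 = 2 × 45/7.5 = 12.0 on 3 df, p = 0.007. Rank-sum p = 0.0006.
- Table B, the same columns reordered: 9/3/12/6 against 6/12/3/9. The deviations are the same in size, so chi-square is again 12.0, p = 0.007. Scoring the bands 0 to 3, both sexes total 45 and average 45/30 = 1.5. Rank-sum p = 1.0.
- Two-way cuts of Table B give chi-square 0.8, 2.4 and 0.8, with p = 0.37, 0.12 and 0.37.

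The four-category test gives the same answer for a clear gradient and for equal means.

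**2. Cut-point and power (simulation).** All inputs are assumptions, none from the documents: whole-point 0-10 scale, normal scores rounded and clipped, SD 2.5, mean 3 in men and 4.5 in women, one rating per patient, two-sided 0.05, no continuity correction, 20,000 trials per setting. The four bands are 0, 1-3, 4-6 and 7-10; the two-way cut is 4 or more.

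| Per sex | Chi-square, each score a category | Four bands | Cut at 4 | Rank-sum | Cuts 3, 4, 5 disagree on p<0.05 |
|---|---|---|---|---|---|
| 20 | 10% | 24% | 30% | 43% | 35% |
| 30 | 18% | 38% | 45% | 59% | 40% |
| 50 | 38% | 62% | 68% | 82% | 38% |
| 100 | 80% | 92% | 93% | 98% | 15% |
| 200 | 99% | 100% | 100% | 100% | 1% |

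The column treating each score as a category is one possible reading only; the documents do not say it was done. At 30 per sex, power of a two-way chi-square is 27% with the cut at 1, 45% at 4 and 31% at 7. For shifts of 1 to 2 points, rank-sum power is 31-84% and that of the cut at 4 is 24-68%.

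Disagreement between cuts means crossing 0.05. In a separate re-run at 30 and 100 per sex (3,000 trials each), no trial had cuts 3 to 5 significant in opposite directions.

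**3. A different effect shape.** Assume instead that 15% of one sex and 45% of the other score 5-8 and the rest score 0-3. At 30 per sex the cut at 4 has about 74% power against about 53% for rank-sum; at 50 per sex, 92% against 76%. The cut lies in the gap between the two clusters, which favours chi-square. It still shows that the ranking in the table belongs to the shift model.

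**4. Cost of five tests.** With five independent null tests, the chance of at least one p<0.05 is 1 − 0.95⁵ = 0.226. With within-patient correlation of 0.3 to 0.7, simulation gives 21% down to 15%.

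**The case against.** The strongest defence is that choosing chi-square implies the scores were grouped, and that chi-square on a grouping fixed in advance is a legitimate test. On that view only a detail is missing. Much of this stands. Chi-square is not invalid in itself, and the documents do not show that raw scores were tabulated. The gap remains, because no grouping is stated under any reading, and grouping either loses order or depends on the cut.

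The defence is also right that the power ranking depends on the assumed shift, that the gap shrinks with numbers, and that proportions by sex printed beside the p-value would show direction. A rank-sum test by sex is also unadjusted for treatment arm and pre-operative pain, so it does not turn a non-randomized comparison into a causal one.

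A reader might infer three stronger things that the documents do not support:

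- **Another cut would reverse the finding.** In the simulation, cuts differ over significance, not over direction.
- **The cut was picked after seeing the data.** The plan does not say when any grouping was fixed; silence is not evidence of selection.
- **The treatment comparison is compromised.** The stated aim concerns the two anesthetics: "there is no evidence that supports the use of one anesthetic solution over the other, which is what this study aims to find". That comparison uses a different test: "Intergroup comparisons were analyzed using a two-sample t-test".

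**Conclusion.** The point holds as a minor one. The outcome is an ordered score, the sex comparison uses a test that needs categories, and neither the grouping nor the hour is given. The loss of order with three or more categories is exact and needs no assumptions.

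The dependence on the cut and the power gap in favour of rank-sum rest on the assumed scale, SD and 1.5-point shift. With no sample size and no numbers of men and women in the documents, the real loss could be substantial or negligible. The consequence is limited to a non-randomized comparison outside the stated aim.

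**What to change.** Compare the numerical scores by sex with a Wilcoxon rank-sum test at each of 6, 12, 24, 48 and 72 hours, one rating per patient per test. At each hour report the Hodges-Lehmann male-female shift with its 95% CI and the numbers of men and women rated. Label all five tests exploratory and, because the text is in the past tense, post hoc.

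If the chi-square result is also reported, state its bands or cut-point, its hour, when these were fixed, and the proportions by sex.

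The cost is a few lines of text and a small re-analysis of questionnaire data already collected. There are two downsides. Five tests carry up to a 23% chance of at least one false positive, which the exploratory label discloses but does not control. On a whole-point scale the Hodges-Lehmann interval is also coarse: under the same assumptions at 30 per sex, its median width is 2 to 3 points, with coverage of 99.5% at no shift and about 95% at a 1.5-point shift.

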Effect of Post-Operative Anesthetics on Post-Operative Pain in Patients Receiving
Endodontic Treatment

NCT05338671

April 8, 2025

Study Protocol and Statistical Analysis Plan:

Participants: Participants were patients of the University of Washington School of Dentistry graduate endodontic clinic.

Exclusion and Inclusion Criteria: Exclusion criteria were the presence of any systemic diseases that precluded the administration of bupivacaine, lidocaine, or ibuprofen, pregnancy, and teeth that had periapical radiolucencies and a pulpal diagnosis of anything other than irreversible pulpitis. Inclusion criteria were healthy adults (18 years or older, ASA I or II), no contraindications to ibuprofen, mandibular posterior teeth with a pulpal diagnosis of irreversible pulpitis (symptomatic or asymptomatic, if pre-operative pain was present), and willing to undergo two-step nonsurgical root canal treatment.

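### The male-female pain comparison leaves out the recorded pre-operative score and does not say how the arms are handled, so any baseline sex difference could carry into it

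*Combined protocol and SAP*

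**What the plan says.** The sex analysis has one clause in the Data Analysis section: "comparisons between male and female post-operative pain levels using the chi-square test". It names no time point, pain category, covariate or arm. The other planned pain analyses are equally brief: "Intergroup comparisons were analyzed using a two-sample t-test, intragroup comparisons using a Wilcoxon signed-rank test". No listed analysis combines sex, arm and pre-operative pain.

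Study Procedures supplies two relevant facts. Before treatment, patients were "given a questionnaire prior to the start of their root canal treatment to rate the pain they were experiencing on a numerical rating scale". Only the anesthetic was allocated at random: "Patients were randomized into either the Bupivacaine group (long-acting anesthetic) or Lidocaine (short-acting anesthetic) group". Stratification by sex is not mentioned.

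Under the eligibility criteria, the irreversible pulpitis may be "symptomatic or asymptomatic, if pre-operative pain was present", so entry pain can vary between patients.

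**The concern.** Randomization gives no assurance that men and women start with the same pain. If post-operative pain tracks pre-operative pain, a gap at entry will show up in part afterwards, even when both sexes recover identically from the same starting pain. A significant chi-square result would then have two readings: one sex has a worse post-operative course, or one sex simply arrived in more pain. The planned test cannot separate them, although the variable that would help is already on the questionnaire.

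A second gap is that the plan does not say whether men and women are compared across both arms together or within each arm. A reader needs to know this to interpret the result.

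What is at stake is the meaning of a secondary comparison, not the trial's main question.

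**Working it through.** **What can be reproduced.** Nothing numerical. The documents give no sample size, significance level, SD, sex split, pain bands or pain scores by sex. The figures below illustrate the mechanism and do not describe this trial's data.

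**Step 1: size of the carry-over.** Assume post-operative pain depends on baseline with coefficient r, with no sex effect beyond baseline. A baseline gap of g points then gives an expected unadjusted post-operative gap of r × g.

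- g = 0: carry-over 0, whatever r is.
- g = 0.5, r = 0.5 to 0.7: 0.25 to 0.35 points.
- g = 1, r = 0.5: 0.5 × 1 = 0.5 points.
- g = 1.5, r = 0.7: 0.7 × 1.5 = 1.05 points.

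Once scores are rounded and held within 0-10, the simulated carry-over for g = 1 to 1.5 is a little smaller, at about 0.4 to 0.9 points.

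**Step 2: how often the tests reject.** All inputs are assumed:

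- baseline SD 2.5, rounded to 0-10
- post-operative score = 3 + r(baseline − 5) + arm effect of 0.5 + noise with SD 2
- r = 0.5 to 0.7
- chi-square on bands 0 / 1-3 / 4 or more, with the arms taken together
- total N of 40, 80 or 120
- two-sided 5% level

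| Baseline gap | Chi-square rejects |
|---|---|
| 0 | about 4-6% |
| 0.5 points | about 5-8% |
| 1 to 1.5 points, N = 40 | about 6-12% |
| 1 to 1.5 points, N = 80 | about 11-24% |
| 1 to 1.5 points, N = 120 | about 14-36% |

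A linear model on sex, arm and baseline score rejects the sex term in about 4-6%, with an estimated sex difference near 0. On the assumed SD of 2.5, gaps of 0.5, 1 and 1.5 points are 0.5/2.5 = 0.2, 1/2.5 = 0.4 and 1.5/2.5 = 0.6 SD.

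**Step 3: a different set-up.** Work in SD units, with baseline gap d, baseline-to-post correlation ρ, equal numbers of each sex, and pain split at its overall midpoint. The carry-over is ρ × d, and the two shares above the midpoint are Φ(−ρd/2) and Φ(ρd/2).

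- Smallest non-zero case: 0.3 × 0.25 = 0.075 SD, shares 48.5% and 51.5%.
- Largest case: 0.7 × 0.5 = 0.35 SD, shares 43.1% and 56.9%.

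With 20 to 50 patients per sex and ρ of 0.3 to 0.7, the unadjusted chi-square rejects in about 4-6% of simulations at d = 0, 5-12% at d = 0.25 and 6-31% at d = 0.5. The baseline-adjusted sex term rejects in about 4.4-5.7% throughout. Direction and rough size agree with Step 2.

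**Step 4: does it depend on pooling?** No. With separate tests in each arm and a gap of 1 to 1.5 points, at least one is significant in about 10-15%, 14-25% and 16-35% of trials at N = 40, 80 and 120. With no gap the figure is 7-11%, because two tests are run.

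**The case against.** The strongest reply is that the plan compares post-operative pain levels by sex and claims nothing about recovery or cause. If one sex really has more pain after treatment, for whatever reason, rejecting equality is correct. On that view the 6-36% is power for the planned comparison. **This stands.** The rejections are false positives only for a different question, namely whether the sexes differ given the same starting pain. The crude comparison remains a valid description, and groups that are not randomized are unavoidable in any comparison by sex.

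Three stronger readings are tempting, and the documents support none of them.

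- **That the arms are pooled.** The clause names no arm, which makes pooling a natural reading, but within-arm tests fit the text too. Pooling would not itself create a baseline sex difference, and randomization balances sex across arms on average, though chance imbalance is possible in a small trial.
- **That a baseline sex difference is in fact being reported as a post-operative one.** No pain score by sex appears anywhere. With no baseline gap there is no carry-over.
- **That leaving out a sex-by-arm analysis is an error.** The stated aim is to choose between two solutions, and no sex-specific treatment claim is planned. An interaction term is a preference and would be imprecise.

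What survives is narrower. The recorded baseline goes unused, the handling of arm is unstated, and nothing marks the sex comparison as exploratory, so a significant result is open to misreading.

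**Conclusion.** The concern holds in this limited form. The planned comparison cannot distinguish a sex difference in post-operative course from one already present at entry, and the data needed to help distinguish them are already held. Whether the problem arises here is unknown.

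Its size depends entirely on the assumed gap: negligible at zero, slight at half a point, and material only at 1 point or more in the larger trials considered. The upper figure of 36% is the worst corner of an assumed grid. The adjusted model performs well partly because the simulation lets the recorded baseline score drive the outcome linearly. With a noisily measured baseline, adjustment would remove less of the carry-over.

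The point is minor. It affects how one secondary result is read and leaves the randomized comparison of bupivacaine with lidocaine untouched.

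**What to change.** 1. Report pre-operative pain by sex, so a reader can see whether there is a gap to carry over.
2. State whether the male-female comparison combines the arms or is made within each, at which time point, and with which pain categories.
3. Estimate the sex difference from one regression of the post-operative score on sex, arm and pre-operative score, with a 95% CI. Show it beside the unadjusted comparison, described as crude post-operative pain by sex.
4. Label the whole sex analysis exploratory.
5. A sex-by-arm term is optional. If it is shown, give its interval and say that it is imprecise.

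The cost is one small table and one regression on data already collected. The sex result may look weaker after adjustment. In the simulations, adjustment also made the standard error of the sex difference about 9-23% smaller, so precision need not suffer.
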